## **10.5** Assessment of Causality

Due to the temporal proximity of an AE to the procedure under investigation, there is a reasonable possibility that the procedure may have caused an AE or may have contributed to the severity or duration of an event caused by other means. Causality to the study procedure or device will be assessed by the PI and relationship will be classified in one of the following categories:

Definitely Not Related	Evidence exists that the adverse event definitely has a cause other than the procedure/device under investigation (e.g. pre-existing condition or underlying disease, intercurrent illness, or concomitant medication) and does not meet any other criteria listed.
Probably Not Related	An adverse event has little or no temporal relationship to the study device/study procedure and/or a more likely alternative etiology exists.
Possibly Related	A temporal relationship exists between the event onset and procedure under investigation, and appears with some degree of certainty to be related based on known therapeutic actions of the procedure/device under investigation. It cannot be readily explained by the patient's clinical state or concomitant therapies.
Probably Related	A temporal relationship exists between the event onset and procedure under investigation, and appears with some degree of certainty to be

- under investigation, and appears with some degree of certainty to be related based on known therapeutic actions of the procedure/device under investigation. It cannot be readily explained by the patient's clinical state or concomitant therapies.
- Definitely Related Strong evidence exists that the procedure/device under investigation caused the adverse event. There is a temporal relationship between the event onset and the procedure under investigation. There is strong therapeutic evidence that the event was caused by the procedure/device under investigation. The patient's clinical state and concomitant therapies have been ruled out as a cause.

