#### **3.2** Primary Safety Endpoints

Incidence of device related adverse events as defined by perforation, instrument separation, root fracture, sodium hypochlorite accident, or Gutta Percha extrusion, as related to the device for the Treatment Complete cohort.

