## 13.6 Safety Analyses

Incidence of device related adverse events as defined by perforation, instrument separation, root fracture, sodium hypochlorite accident or Gutta Percha extrusion, as related to the device will be summarized for the Safety Population.

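### Possibly Related and Probably Related have the same definition, some events fit no causality level, and no cut for device related is stated, so the primary safety count is not reproducible

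*Combined protocol and SAP*

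**What the plan says.** Section 10.5 asks the investigator to place each adverse event in one of five causality levels. From the bottom up:

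- **Definitely Not Related** is worded as follows: "Evidence exists that the adverse event definitely has a cause other than the procedure/device under investigation".
- **Probably Not Related** has this wording: "An adverse event has little or no temporal relationship to the study device/study procedure and/or a more likely alternative etiology exists". It is the upper of the two unrelated levels.
- **Possibly Related** is the first level on the related side, and its text begins: "A temporal relationship exists between the event onset and procedure under investigation, and appears with some degree of certainty to be related". The judgement rests on the known actions of the procedure or device, with the added condition: "It cannot be readily explained by the patient's clinical state or concomitant therapies".
- **Probably Related** repeats the two sentences of the level below it.
- **Definitely Related** needs strong evidence of causation, with other causes ruled out.

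The same section opens by accepting that the procedure "may have contributed to the severity or duration of an event caused by other means".

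The primary safety endpoint in section 3.2, repeated in the synopsis, is "Incidence of device related adverse events as defined by perforation, instrument separation, root fracture, sodium hypochlorite accident". Gutta Percha extrusion is the fifth event type, and all five are counted where related to the device. Section 13.6 says that these events, "as related to the device will be summarized for the Safety Population". Neither section names the causality levels that make an event device related. Section 10.3 has the investigator record the relationship to the procedure and to the device. Sections 7.7 and 10.5.1 define when GentleWave Treatment begins and ends, and class every other step as traditional root canal therapy.

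**The concern.** A five-level scale is useful only if each level has its own meaning and every event has a place. Here the weakest related level carries the condition that one would expect of the stronger one. The five levels amount to four, and the place where ambiguous events would normally go is missing.

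This matters because the rating decides what enters the numerator of a primary endpoint. The treating investigator assigns it, and the documents describe no independent adjudication. Ambiguous attribution is foreseeable: every subject also has conventional access, shaping and obturation, and section 10.8.2 lists perforation and instrument separation as risks of root canal therapy in general. Two investigators who see the same event could file it differently, both within the text, and the reported incidence would depend on which of them saw it.

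**Working it through.** The plan gives no figure for this point: no expected event rate, no safety threshold and no causality cut. The check is therefore mainly one of wording.

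**1. Are the two definitions the same?** The Probably Related row runs over a page break, where 68 characters are repeated. After the break it continues "under investigation, and appears with some degree of certainty to be related based on known therapeutic actions of the procedure/device under investigation" and ends with the same condition on alternative explanations. With the repeated characters removed, the row matches Possibly Related character for character. The Possibly Related row is unbroken and reads as complete. The match should still be confirmed in the source PDF.

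**2. Does every event have a level?** Take an event that follows treatment and sort it by its alternative explanation, with Definitely Related left aside.

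| Alternative explanation | Level that fits |
|---|---|
| Definite other cause, with evidence | Definitely Not Related |
| More likely than the procedure or device | Probably Not Related |
| Ready, but equally or less likely | None |
| None that readily explains it | Possibly or Probably Related, indistinguishable |

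In the third row, the ready explanation bars both Possibly and Probably Related. Probably Not Related fails because the timing fits and the alternative is not the more likely one. Definitely Not Related fails because no other cause is established. This gap also sits badly with the section's opening, which accepts contributory causation.

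**3. What happens to the count?** That depends on the cut, which is not stated.

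- *Possibly, Probably and Definitely count.* The duplicate wording alone moves no event across the line. A gap event is counted if the investigator chooses Possibly Related, and not if the choice is Probably Not Related.
- *Only Probably and Definitely count.* The line falls between two levels with one definition. The split is arbitrary and can err either way.
- *Only Definitely counts.* Neither defect changes the count.

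**4. Scale.** Section 13.1 plans 108 subjects and about 86 evaluable (108 × 0.80 = 86.4). Moving one event into or out of the numerator changes the incidence by:

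- 1/86 = 0.0116, or 1.2 percentage points;
- 1/108 = 0.0093, or 0.9 percentage points.

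Both denominators are shown because section 3.2 uses the Treatment Complete cohort and section 13.6 the Safety Population; neither planned number need equal the final denominator. The shift can go in either direction. The number of events affected cannot be derived from the documents.

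**The case against.** A reader might infer that the endpoint is undercounted, and that the investigator has to rate a gap event as not related. The documents support neither. Probably Not Related sets a condition that such an event does not meet, so nothing compels that rating, and the opening of section 10.5 leans towards recognising a contribution from the procedure. With no stated cut, no direction of bias follows. Confidence limits for invented event counts would not help: they show the imprecision of a small sample, not the effect of this wording.

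The gap is also narrow. Having some competing explanation does not exclude an event from the related levels; it must be one that readily explains the event. An event with a more likely alternative does have a level.

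The consequences are limited too. Section 13.6 plans a descriptive summary with no test or success threshold. Section 10.3 requires a relationship rating and a narrative for every event, so results could be shown by level. Section 13.0 leaves analysis details to a statistical analysis plan, and a cut might be stated there, although none appears in the text available.

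These arguments narrow the point but do not remove it. Narratives and tables by level cannot restore a distinction that the definitions never made, and a later analysis plan can set a cut but cannot change how investigators were told to rate.

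**Conclusion.** The point holds as a defect of definition. Two of the five levels cannot be distinguished, a temporally related event with a plausible but not more likely alternative has no level, and the documents do not say which levels make an event device related. The numerator of the primary safety endpoint is therefore not reproducible. It may be too low, because the weakest related level carries the excluding condition, but that is a risk and not a demonstrated result.

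The per-event shifts above give scale only and do not estimate a bias. The efficacy sample size is unaffected. The conclusion rests on two assumptions: that the source PDF shows the same duplicate text, and that no separate analysis plan states the cut. If such a plan does state it, the duplicate definitions and the gap remain. The correction is worth making because a primary endpoint depends on the rating, but the plan does not fail on it.

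**What to change.** 1. In section 10.5, redefine Possibly Related as the weaker level: the timing fits, but the event could also be explained by the patient's clinical condition, another treatment or another cause that is not more likely. Keep the present text for Probably Related. This separates the two levels and closes the gap.
2. In sections 3.2 and 13.6, and in the synopsis, state that events rated Possibly, Probably or Definitely Related to the device count as device related.
3. Tie that cut to the separate device rating collected under section 10.3, not to the rating for the procedure or for traditional root canal steps. Section 10.5 speaks of procedure and device together on one scale, so a cut without this limit would bring in events tied only to conventional steps.
4. Report the five event types by causality level as well, so that a reader can apply another cut.

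The cost is one definition, one sentence for the cut and guidance on the case report form. Events already rated under the present text would need to be rated again. Visits, treatment and sample size do not change. The downside is that the reported device-related rate may rise slightly.

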# 10.5.1 Definition of Sonendo GentleWave System Treatment

The Sonendo GentleWave System Treatment is defined as beginning when LuxaBite or a Tooth Cap is placed until 100% completion of the Sonendo GentleWave System. All other procedures will be categorized as traditional RCT procedures.

# 10.6 Serious Adverse Event Reporting

PIs must report all Serious Adverse Events (SAEs) to the Sponsor within a timely manner of observing or learning of the event. For initial SAE reports, Investigators should record all case details that can be gathered within a timely manner on the SAE CRF and fax this information immediately upon completion to the Sponsor. The fax number is [contact].

Each SAE must be followed with appropriate medical management until it's resolved or assessed as chronic or stable regardless of whether or not, in the opinion of the Investigator, the event is

thought to be related to the procedure. The Investigator will be required to provide complete information concerning each SAE to the sponsor within in a timely manner. This information must be recorded in the subject's medical record and then transcribed onto the Adverse Event CRF. The completed Serious Adverse Event Report (SAE) (including the Investigator's opinion of the relationship of the SAE to the procedure/device under investigation), copies of related results/reports, consultant report(s), and other relevant information will be faxed and/or mailed to the Sponsor.

All SAEs as described above, covering the period from a subject's enrollment in the study through seven (7) days following a subject's completion as per protocol or premature discontinuation from the trial will be managed and reported. The decision to report potential SAEs beyond the seven (7) day post-study period will be at the discretion of the Sponsor, unless otherwise advised by the IRB.

In addition, Investigators must report all SAEs to their Institutional Review Board (IRB) and regulatory bodies according to applicable guidelines and regulations. A copy of the notification must also be submitted to the Sponsor.

# **10.7** Unanticipated Adverse Device Effect

Pursuant to Part 812.3(s) of Title 21 of the Code of Federal Regulations, the definition of an Unanticipated Adverse Device Effect (UADE) means any serious adverse effect (as defined above) on health or safety or any life-threatening problem or death caused by, or associated with a device, if that effect, problem, or death was not previously identified in nature, severity or degree of incidence in the clinical protocol or application (including a supplementary plan or application), or any other unanticipated serious problem associated with a device that relates to the rights, safety, or welfare of subjects.

Any UADE must be reported to the Sponsor either by [contact] or [contact] within 24 hours of knowledge of that event. In addition, Investigators must report all UADEs to the IRB and regulatory bodies according to applicable guidelines and regulations.

The Sponsor will be responsible for informing Regulatory Authorities, all other IRBs, and Investigators participating in the study of the UADE according to the applicable guidelines and regulations.

# **10.8** Anticipated Adverse Events

10.8.1 Risks generally associated with any dental procedure include, but are not limited to, the following:

• Pain and/or discomfort

Numbness

- Swelling or inflammation
- Pressure

- Paresthesia (tingling)
- Post-treatment infection

- Abscessed tooth
- Bleeding
- Tooth color changes
- Potential for re-treatment
- Reoccurring decay
- Reaction to medications or anesthesia
- Reaction to materials or chemicals used
- Sensitivity to hot and/or cold air

10.8.2 Potential risks for root canal therapy include, but are not limited to, the following:

- Post-treatment pain and/or discomfort
- Post-treatment swelling or inflammation
- Pressure
- Numbness
- Paresthesia (tingling)
- Post-treatment infection
- Abscessed tooth
- Bleeding
- Tooth color changes
- Potential for re-treatment
- Reoccurring decay
- Reaction to medications or anesthesia
- Reaction to materials or chemicals used
- Extrusion of debris into the periapical tissue

pressure or sweets

- Breakdown of the inner filling causing infection and/or damage
- Weakening of the tooth
- Instrument breakage within the canal
- Perforating (creating a small hole) the side of the root
- Tissue damage
- Tooth crown fracture or breakage
- Sensitivity to hot and/or cold, air pressure or sweets
- Breakdown of the inner filling causing infection and/or damage
- Defective or inadequate restoration of the tooth which could lead to infection, leakage, loosening, detachment, or breakage
- Uninstrumented recesses of the tooth (i.e. missed canals or uncleaned areas)
- Instrument separation (i.e. breakage within the canal)
- Perforating (creating a small hole) the side of the root
- Damage to sinus floor or sinus infection
- Tissue damage
- Root weakening
- Ledge formation

- Weakening of the tooth
- Jaw bone infection or damage
- Worn out filling

## **10.9 Other Potential Risks**

#### 10.9.1 Radiation Risks

Radiation exposure will occur during radiograph examinations. Exposure to ionizing radiation while a low risk, has the potential to cause cancer and other risks.

There are also additional fetal risks associated with ionizing radiation exposure. Ionizing radiation is utilized in diagnostic procedures, such as radiographs, because without these procedures diagnostics on pulp diseases and other conditions would not occur.

## 10.9.2 Cone Beam Computed Tomography (CBCT) Radiation Risks

Although the radiation doses from dental CBCT exams are generally lower than other cone beam exams, dental CBCT exams typically deliver more radiation than conventional dental radiographic exams.

## 10.9.3 Pregnancy (risks for the fetus)

As dental procedures are associated with risks for pregnant women and the fetus, pregnant women will not be included in this research study. It will be recommended for subjects to avoid becoming pregnant during the study.

If a subject becomes pregnant during the duration of the study, the clinical site will document the pregnancy with a Memo to File. Study required radiographs or cone beam will not be collected for pregnant subjects but these subjects will still be followed for the duration of the study. The clinical site designee will not complete a Protocol deviation CRF for study required radiograph assessment not completed due to pregnancy. A Memo to File documenting this deviation will suffice.

## **10.10** Definitions of Adverse Events

## Sodium Hypochlorite Accident is defined as follows: 69, 70

Inadvertent extrusion of sodium hypochlorite past the protective apical constriction or through a lateral canal or root perforation which results in bleach injury as characterized by severe intermittent and/or constant pain, profuse bleeding combined with extraoral or facial swelling, edema, ecchymosis, and/or oral or facial parasthesia.

## Extrusion of Filling Materials is defined as follows: 71, 72

- Tooth root fracture or breakage
- Tooth crown fracture or breakage

Gross overextension of the filling materials beyond the confines of the root canal and into the surrounding vital structures resulting in post operative discomfort, pain, parasthesia and/or anesthesia.

## 11.0 BENEFITS

The potential benefits of the Sonendo GentleWave treatment include the following:

- Significantly reduced pain
- Provide long-term pain relief
- Improved quality of life

These benefits are consistent with the effectiveness criteria studied in similar devices.

## **12.0 PROTOCOL DEVIATIONS**

A protocol deviation is defined as an event where the PI or clinical site designee did not conduct the study according to the Clinical Protocol.

A clinical designee should notify the Sponsor of any protocol deviation(s), preferably via email. Deviations must be reported to the Sponsor regardless of whether medically justifiable, preapproved by the Sponsor, or taken to protect the subject in an emergency. PIs must also adhere to procedures for reporting protocol deviations to the IRB in accordance with their specific IRB's reporting policies and procedures.

Regulations require that PIs maintain accurate, complete and current records, including documents showing the dates of and reasons for each deviation from the protocol. For reporting purposes, the Sponsor classifies study deviations as major and minor:

- Major deviation: Any deviation from subject's Inclusion and Exclusion Criteria, subject's informed consent procedures or unauthorized device use. This also includes enrollment in another clinical study within 30 days of enrollment.
- Minor deviation: Deviation from a protocol requirement such as incomplete/inadequate subject testing procedures, follow-ups performed outside specified time windows, etc.

It is untimely the PI's responsibility to determine the protocol deviation classification.

## 12.1.1 Protocol Deviation Types

The Sponsor has designated the following protocol deviation types for reporting purposes:

- Deviation from Informed Consent Process
- Patient did not meet Inclusion and/or met Exclusion Criteria
- Patient study visit out of study window
- Patient missed a study visit

- Assessment/Questionnaire was not completed
- Assessment/Questionnaire was completed out of study window
- Other

## **13.0 STATISTICAL METHODS**

All required data for this study will be collected on paper or electronic Case Report Forms (CRFs). The Investigator (or designated study staff) will assure primary data collection based on source documented dental chart reviews. Independent monitoring will be performed to ensure that the investigator and his/her study team conducted the clinical investigation in accordance with contract specifications, study protocol, Declaration of Helsinki, and applicable local or national regulations, to ensure adequate protection of the rights and safety of subjects and the quality and integrity of the resulting data.

In general, quantitative variables will be summarized to indicate the population sample size (N), number of patients with available data (n), mean, standard deviation, median, minimum, and maximum values. Qualitative variables will be summarized by the population size (N), number of patients with available data (n), number of patients in each category, and the percentage of patients in each category. Analyses will be based on the Safety Population defined as all patients who receive the Sonendo GentleWave System procedure. Details of analysis methods will be described in the statistical analysis plan.

## 13.1 Sample Size

All patients will receive root canal therapy with the Sonendo GentleWave System and will be subsequently followed for 24 months post procedure. A sample size of 108 subjects, assuming a 20% lost to follow-up or Treatment Incomplete Cohort rate, will result in approximately 86 subjects who would be evaluable for the primary efficacy endpoint. A sample size of 86 evauable subjects provides approximately 90% power to detect a difference between a 85% response rate for subjects using the Sonendo GentleWave System against a null hypothesis of a 70% response rate based on data presented in literature for traditional root canal therapy, using a two-sided binomial test at the 5% level of significance.

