## 2.3 Healing Rates for Traditional Root Canal Therapy

While the literature presents many different definitions of healing, any future endodontic clinical studies should utilize a healing endpoint based upon both clinical and radiographic findings. The radiographic finding should be based upon the periapical index score, with PAI 1 or 2 indicating success. Additionally, no clinical signs or symptoms should be present. Separating complete healing and incomplete healing will also more clearly present study results.

Success rates over time varied widely across the literature. Generally, most healing had occurred 1 year following root canal treatment, though healing was shown to take up to 4 years or more. Thus, success rates should also be presented at each time-point studied and not just a cumulative number over a range of follow-up periods. An approximate success rate for 1 year follow-up would be 68-70% while that success rate would increase to 80-85% after four years.

While effective chemomechanical canal preparation is extremely important, the literature indicated other factors significantly affected long-term prognosis for the patient. If a patient presented with apical periodontitis and had a periapical lesion, the long-term success was significantly lower. Thus, including a large number of patients with a pre-operative periapical radiolucency could result in lower long-term success rates. Effective obturation to within 2 mm within the radiographic apex and effective coronal restorations also improved long-term success. The number of roots treated and mid-treatment complications could also impact success rates. These facts highlight the importance of choosing the appropriate patient

population and standardizing the treatment regimen in clinical studies so that the variable being studied can be reliably assessed.

While a number of studies have been published regarding the healing and success rates following root canal treatment, the quality of this literature is generally less than other medical disciplines. A dearth of randomized, controlled trials exists in endodontic research, and a large number of retrospective studies are published. Finally, the lack of standardization of study design and clinical endpoints across studies makes the comparison of results between studies difficult at best. *(See Appendix I. Healing Literature Report)* 

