#### **3.1** Primary Effectiveness Endpoints

Subject teeth in the Treatment Complete cohort that are healed or are healing at the twentyfour month Follow-up Visit.

Healed is defined by absence of a radiographic indication of apical periodontitis (PAI <3) and absence of clinical signs and symptoms.

Healing is defined by a reduction of radiolucency (if radiolucency is present at Baseline) and/or reduction of clinical signs and symptoms (if clinical signs and symptoms are present at Baseline)

Secondary analysis will be performed after all Treatment Complete subjects have completed the 12 month Follow-up Visit.

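### The 70% literature null in 13.1 carries no follow-up time, source or success definition; in the visible text it matches only the 1-year rate, so for a 24-month endpoint it may be too low

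*Combined protocol and SAP*

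**What the plan says.** Section 13.1 plans 86 evaluable subjects for about 90% power at a true response rate of 85%, "against a null hypothesis of a 70% response rate based on data presented in literature for traditional root canal therapy", with a two-sided 5% binomial test. It attaches no follow-up time, specific source or definition of success to the 70%.

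The endpoint in 3.1 is "Subject teeth in the Treatment Complete cohort that are healed or are healing at the twentyfour month Follow-up Visit". Besides healed teeth it counts teeth that are only healing: "Healing is defined by a reduction of radiolucency (if radiolucency is present at Baseline) and/or reduction of clinical signs and symptoms". Section 13.4 reports the 24-month proportion with an exact 95% confidence interval. It names neither a benchmark nor a success criterion, and 13.0 leaves details of the methods to the statistical analysis plan.

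The dated literature figures are in 2.3: "An approximate success rate for 1 year follow-up would be 68-70% while that success rate would increase to 80-85% after four years". On the time course, 2.3 says: "Generally, most healing had occurred 1 year following root canal treatment, though healing was shown to take up to 4 years or more". It recommends that "success rates should also be presented at each time-point studied and not just a cumulative number over a range of follow-up periods". On the definition of success it says "The radiographic finding should be based upon the periapical index score, with PAI 1 or 2 indicating success", together with no clinical signs or symptoms. The section closes with a pointer to the literature review ("See Appendix I. Healing Literature Report").

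**The concern.** The literature control is the trial's only comparison, so the benchmark decides what a positive result means. The endpoint is read at 24 months, and in the visible text 70% coincides only with the top of the 1-year range. The same section says the rate goes on rising to year four. If the 70% is a 1-year rate, healing that traditional therapy also achieves between months 12 and 24 would be counted in favour of the device. The stated 5% level and 90% power would then not describe the 24-month comparison.

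Leaving the benchmark undated also departs from 2.3's own advice to report success by time-point. The definition needs stating too. Section 2.3 recommends a strict one, while the endpoint adds partially improved teeth. If the 70% was built on the strict definition, a like-for-like rate would be higher.

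**Working it through.** **Inputs.** From 13.1: null 70%, alternative 85%, n = 86, two-sided 5% (0.025 per tail), 20% loss. From 2.3: 68-70% at 1 year and 80-85% at four years. From the synopsis and 5.0: a cap of 120 subjects.

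**1. The plan's own figure.** Let X ~ Binomial(86, p). The smallest x with P(X ≥ x | p = 0.70) ≤ 0.025 is 69, where the tail is 0.0223. The exact 95% lower limit is 0.7025 at 69/86 and 0.6895 at 68/86, so requiring a lower limit above 70% gives the same rule, at least 69 of 86. Power is P(X ≥ 69 | 0.85) = 0.914, in line with the stated 90%. Enrolment: 86/0.8 = 107.5, rounded up to 108. The sample size is right for its inputs; the question is the null.

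**2. What a 24-month traditional rate might be.** The documents give none. Straight-line interpolation, one third of the way from year 1 to year 4, gives:
- low ends: 68 + (80 − 68)/3 = 72%
- high ends: 70 + (85 − 70)/3 = 75%

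This is an assumption. A value of 71% is added to represent a rate only slightly above 70%.

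**3. Chance that a device no better than traditional therapy passes, and power against a corrected null.** The second column is P(X ≥ 69 | p), with the true device rate p equal to the traditional rate. The last two columns recompute the critical count for that null at n = 86 and the power at 85%.

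| 24-month traditional rate | Passes the 69/86 rule | Critical count if used as null | Power at 85% |
|---|---|---|---|
| 70% | 2.2% | 69 | 91% |
| 71% | 3.5% | 70 | 86% |
| 72% | 5.3% | 71 | 79% |
| 75% | 16% | 73 | 59% |

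**4. Can enrolment restore 90%?** The cap gives at most 120 × 0.8 = 96 evaluable, and fewer if roll-in subjects, whom the synopsis and 19.1 allow to be left out of the analysis, are excluded. At n = 96, power at 85% is 87.8% against 71%, 81% against 72% and 63% against 75%. Exact power moves in steps. Against 71% it first touches 90% at n = 93, drops below at 94 to 96, and stays at or above 90% only from n = 101. The first n reaching 90% is 109 against 72% and 174 against 75%. Within the cap, 90% is therefore not dependably recoverable even against 71%.

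**The case against.** Four points weigh on the other side.

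- **Appendix I is unseen.** It is where the plan keeps its benchmark evidence, and it may well give 70% at 24 months. Its absence from the text available for review is not a fault in the plan. This stands, and it makes the point conditional. It does not remove the need for 13.1 to say which rate it uses.
- **The gap may be small, or case mix may close it.** Section 2.3 says most healing has occurred by 1 year, that periapical lesions lower long-term success, and that the number of roots matters. The trial takes only first and second molars and does not exclude periapical lesions, while 2.3 does not say its rates are molar-specific. It also calls the rates approximate and comparison across studies difficult. This stands. It is why the conclusion is that the benchmark may be too low, and no more.
- **The pass rule is implied.** Section 13.4 promises only a proportion and an interval, which can be read against any benchmark. This stands. The false-pass figures depend on reading 13.1's test as the decision rule; the effect on planned power does not.
- **The definition mismatch has no known size.** Section 2.3 does not say which definition underlies 68-70%. This stands, so the definition should be stated and no adjustment is claimed.

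A reader might infer that the 70% is the 1-year rate and the null is therefore wrong. The match is an inference, and Appendix I could refute it. A reader might also use a curve that rises faster early on, for example linear in log-time. With the top of both ranges that gives 70 + 15/2 = 77.5% at year 2, and a false-pass rate of about 32%. No such curve appears in the documents, so that figure is not relied on here.

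**Conclusion.** The point holds in conditional form. The null is undated, unsourced and undefined in 13.1, the endpoint is at 24 months, and the visible text ties 70% only to 1 year. Unless Appendix I supports 70% at 24 months under a comparable definition, the benchmark may be too low and favour the device.

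The size is unknown. Across true traditional rates of 70% to 75%, the chance that an equivalent device passes runs from 2.2% to 16%, and power at 85% against a corrected null runs from 91% down to 59%. These figures assume the 69/86 rule, 86 evaluable subjects and, for 72-75%, straight-line interpolation. The documents do not establish that the benchmark is wrong, nor that the gap is large. The matter should be fixed because it concerns the trial's only decision threshold and the change is cheap. Confidence is medium.

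**What to change.** Keep the 24-month endpoint.

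- **13.1:** state the benchmark's source, follow-up time and success definition. If Appendix I gives 70% at 24 months under a comparable definition, cite it and keep the stated power.
- **If it does not:** replace 70% with a sourced 24-month rate for a comparable population and definition, and restate the power of 86 evaluable subjects at 85% (about 86% against 71%, 79% against 72%, 59% against 75%). Do this before the 12-month analysis announced in the synopsis and 3.1, and before any look at outcome data. In an open single-arm trial, a benchmark changed after that look could be informed by the results. (Section 13.5 places the secondary analysis at 24 months; the earlier date is the safe one.)
- **13.4:** state that success means the lower limit of the exact 95% confidence interval exceeds that benchmark. Any comparison with a 1-year 70% should use the 12-month visit data and be supportive only.

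The cost is one citation if 70% has a 24-month source. Otherwise it is a change of wording in 13.1 and 13.4 and a less favourable stated power, with no added enrolment.
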